1 INTRODUCTION

Major changes to the protocol-planned analyses are described in [Section 3.9](#).

1.1 STUDY DESIGN

This is a parallel group, phase 2, randomized, double-blind, placebo controlled, dose-ranging study, international, multicenter, 12-week study. It is designed to assess the therapeutic dose, efficacy, and safety of treatment with SAR441566 in male and female adults with moderate to severe plaque psoriasis.

Study details include:

- Screening period (4 weeks and not less than 11 days before Day 1).
- Treatment period (12 weeks ± 3 days).
- Post-treatment period (safety follow-up) (4 weeks ± 3 days).
- The total number of study visits will be 7.

Participants who satisfy the inclusion and exclusion criteria will be randomized to either SAR441566 or matching placebo, administered orally for 12 weeks.

Visits during the 12-week treatment period will occur at Week 0 (baseline/randomization), 2, 4, 8, and 12 weeks, followed by a 4-week post-treatment period if enrolled under the protocol dated 04-Dec-2023 or after, otherwise by a 2-week post-treatment period.

[figure not shown]
Approximately 207 adult participants who meet the inclusion/exclusion criteria will be randomized to either SAR441566 or matching placebo in two different strata, ie, Naive Targeted Immunotherapy Population (NTIP) and Experienced Targeted Immunotherapy Population (ETIP).

- NTIP: Approximately 144 participants will be randomized to either SAR441566 or matching placebo (120 in the five SAR441566 groups and 24 in the placebo group) in this stratum. This population is the primary population for efficacy analysis.
- ETIP: Approximately 63 participants will be randomized to either SAR441566 or matching placebo (54 in the three SAR441566 groups and 9 in the placebo group) in this stratum. This population is for exploratory purposes only.

In the NTIP, there are 6 arms in this stratum with parallel groups of 200 mg bis in die (BID) (n=24), 100 mg BID (n=24), 200 mg quaque die (QD) (n=24), 100 mg QD (n=24), 50 mg QD (n=24), or placebo (n=24), at a randomization ratio of 1:1:1:1:1:1. Duration of investigational medicinal product (IMP) treatment is 12 weeks. (See [Figure 1](#) for schema).

In the ETIP, there are 4 arms in this stratum with parallel groups of 200 mg BID (n=18), 200 mg QD (n=18), 100 mg QD (n=18) or placebo (n=9), at a randomization ratio of 2:2:2:1. Duration of IMP treatment is 12 weeks. (See [Figure 1](#) for schema).

Figure 1 - Graphical study design

[figure not shown]

Study primary analysis will be conducted after study completion.

1.2 OBJECTIVES AND ENDPOINTS

Table 1 - Objectives and endpoints

	Objectives	Endpoints
Primary	
 To demonstrate the superiority of SAR441566 over placebo in participants with moderate to severe plaque psoriasis, in the NTIP. 	
 Proportion of participants with a 75% or greater PASI score (Psoriasis Area and Severity Index score) improvement (reduction) from baseline (PASI75) at Week 12.
Secondary	
 To evaluate the efficacy of SAR441566 in plaque psoriasis as compared to placebo in the NTIP. 	
 PASI percent change from baseline to Week 12. Proportion of participants with static Psoriasis Global Assessment (sPGA) score 0 (complete clearance) or 1 (minimal disease) at Week 12.

Objectives	Endpoints

• To evaluate the safety of SAR441566.• To assess pharmacokinetics of SAR441566 in participants with moderate to severe plaque psoriasis.	
• Incidence of TEAE, SAEs, and AEs of AESIs.• Incidence of study IMP permanent discontinuations and study withdrawals due to TEAEs.• Participants with medically significant changes in vital signs, ECG, and/or laboratory evaluations.• Plasma pre-dose and post-dose concentrations of SAR441566.
Tertiary/Exploratory	

• To evaluate the efficacy of SAR441566 in plaque psoriasis as compared to placebo change over time.	
• PASI percent change from baseline to Week 4 and 8.   
• The proportion of participants with a 90% or greater PASI reduction from baseline (PASI90) at Week 4, 8 and 12.   
• The proportion of participants with PASI75 at Week 4, and 8.     

• To characterize the pharmacodynamic profile of SAR441566 in participants with plaque psoriasis.	
• Change in peripheral blood soluble biomarkers (including but not limited to hsCRP, IL-17A, IL-17F, 

Objectives	Endpoints

• To evaluate the impact of SAR441566 on health	
• Change in Dermatology Life Quality Index (DLQI)

1.2.1 Estimands

Primary estimands defined for main endpoints are summarized in [Table 2](#) below. More details are provided in [Section 3](#).

For all these estimands, the comparison of interest will be the comparison of SAR441566 vs. placebo.

Table 2 - Summary of primary estimand for main endpoints

Endpoint Category (estimand)	Estimands			
	Endpoint	Population	Intercurrent event(s) (ICE) handling strategy	Population-level summary (Analysis and missing data handling)
Primary objective: To demonstrate the superiority of SAR441566 over placebo in NTIP with moderate to severe plaque psoriasis.				
Primary endpoint (treatment policy/composite estimand)	Proportion of participants with	NTIP	Initiation of selected concomitant	Difference in the percentage of participants achieving

Endpoint Category (estimand)	Estimands			
	Endpoint	Population	Intercurrent event(s) (ICE) handling strategy	Population-level summary (Analysis and missing data handling)
PASI75 response at Week 12.			medication ¹ : It will be handled with the composite strategy, ie, participants will be considered as non-responders after such event.	PASI75 response at Week 12 between each active arm and placebo. Testing for odds ratio using the Cochran-Mantel-Haenszel test.
			Discontinuation of IMP: It will be handled with the treatment policy strategy. The primary endpoint will be assessed based on all assessments irrespective of the IMP discontinuation.	After applying the rules for the ICEs, the remaining missing data will be handled as follows: - Participants will be considered as non-responders
Secondary objective: To evaluate the efficacy of SAR441566 in plaque psoriasis as compared to placebo in the NTIP.				
Secondary endpoint (treatment policy/composite estimand)	PASI percent change from baseline to Week 12.	NTIP	Initiation of selected concomitant medication ¹ : It will be handled with the composite strategy WOCF (Worst Observation Carried Forward), ie, data after the concomitant medication use will be assigned using the worst postbaseline value on or before the time of the medication usage.	Mean difference in PASI percent change from baseline to Week 12 between each active arm and placebo, using ANCOVA analysis.
			Discontinuation of IMP: It will be handled with the treatment policy strategy. The endpoint will be assessed based on all assessments irrespective of the IMP discontinuation.	After applying the rules for the ICEs, the remaining missing data will be handled as follows: - "Worst observation carried forward" (WOCF) approach will be used to impute missing data

Endpoint Category (estimand)	Estimands			
	Endpoint	Population	Intercurrent event(s) (ICE) handling strategy	Population-level summary (Analysis and missing data handling)
	Proportion of participants with sPGA score 0 or 1 at Week 12.	NTIP	
Initiation of selected concomitant medication¹: It will be handled with the composite strategy, ie, participants will be considered as non-responders after such event.
 
Discontinuation of IMP: It will be handled with the treatment policy strategy. The endpoint will be assessed based on all assessments irrespective of the IMP discontinuation.
	
Difference in the percentage of participants with sPGA score 0 or 1 at Week 12 between each active arm and placebo.
 
Testing for odds ratio using the Cochran-Mantel-Haenszel test.
 
After applying the rules for the ICEs, the remaining missing data will be handled as follows:
 
 - Participants will be considered as non-responders

¹Selected concomitant medication are listed in [Table 4](#).

2 ANALYSIS POPULATIONS

The following populations for analyses are defined.

Table 3 - Populations for analyses

Population	Description
Screened	All participants who signed the ICF.
Randomized	All participants from screened population who have been allocated to a randomized intervention by IWRS regardless of whether the intervention was received.
Intent-to-treat (ITT)*	All randomized participants. Participants will be analyzed according to the intervention allocated by randomization.
Safety	All randomized participants who have taken at least 1 dose of study intervention, regardless of the amount of treatment administered. Participants will be analyzed according to the intervention they received, ie, "as treated" group.
Pharmacokinetic (PK)	All participants from the safety population with at least one post-baseline PK result with adequate documentation of dosing and sampling dates and times. Participants having received only placebo will not be part of the PK population. Participants will be analyzed according to the intervention they received.
Pharmacodynamic biomarker (PDy) population	All randomized participants who (a) had at least one dose of study intervention (SAR441566 or placebo) and (b) had a sample drawn for biomarker measurement and successfully analyzed at baseline and at one or more post-baseline visits. The assignment of patients to interventions will be "as treated".
NTIP	All randomized participants who have never received targeted immunotherapy for psoriasis. Participants will be analyzed according to the intervention allocated by randomization.
ETIP	All randomized participants who previously received targeted immunotherapy for psoriasis. Participants will be analyzed according to the intervention allocated by randomization.

* Randomized population and ITT population are the same population in this study.

Participants exposed to study intervention before or without being randomized will not be considered randomized and will not be included in any analysis population. The safety experience of these participants will be reported separately.

Randomized participants for whom it is unclear whether they took the study intervention will be considered as exposed and will be included in the safety population as randomized.

For any participant randomized more than once, only the data associated with the first randomization (except if the first randomization is done by error) will be used in any analysis population. The safety experience associated with any later randomization will be reported separately.

For participants receiving more than one study intervention during the study, the intervention group for "as-treated" analyses will be the intervention group as randomized if the participant received at least one administration as randomized.

If a participant is stratified incorrectly at randomization, the participant will be analyzed as stratified per the ITT principle.

3 STATISTICAL ANALYSES

3.1 GENERAL CONSIDERATIONS

In general, continuous data will be summarized using the number of observations available, mean, standard deviation (SD), median, Q1, Q3, minimum, and maximum. Categorical and ordinal data will be summarized using the count and percentage of participants. The graphical plots will be presented for selected endpoints including primary, secondary and some exploratory endpoints.

The baseline value is defined as the last available value before the first dose of double-blind investigational medicinal product (IMP). For participants randomized but not treated, the baseline value is defined as the last available value before randomization.

Unless otherwise specified, analyses will be performed by intervention group/dose level (and overall for baseline and demographics characteristics).

Observation period

The observation period will be divided into 4 segments:

- The **pre-treatment period** is defined as the period up to first double-blind investigational IMP administration.
- The **treatment-emergent (TE) period** is defined as the period from the first IMP administration to the last IMP administration + 5 days. The treatment-emergent period includes the following 2 periods:
 - The **on-treatment period** is defined as the period from the first IMP administration to the last administration of the IMP + 1 day.
 - The **residual treatment period** is defined as the period from the end of the on-treatment period to the end of the treatment-emergent period.
- The **post-treatment period** is defined as the period from the end of the treatment-emergent period.

3.2 PRIMARY ENDPOINT(S) ANALYSIS

The primary endpoint is the response in PASI75, which is defined by proportion of participants with a 75% or greater PASI improvement (reduction) from baseline at Week 12.

3.2.1 Definition of endpoint(s)

The primary endpoint is defined based on psoriasis area and severity index (PASI) as explained below.

Psoriasis area and severity index (PASI)

The PASI is an established measure of clinical efficacy for psoriasis medications. The PASI is a tool that provides a numeric scoring for participants' overall psoriasis disease state, ranging from 0 to 72. Higher scores indicated greater Psoriasis severity. It is a linear combination of percent of surface area of skin that is affected and the severity of erythema, induration, and desquamation over four body regions.

The endpoints used are based on the percent reduction from baseline, generally summarized as a dichotomous outcome based on achieving over an X% reduction (or PASIX), where X is 50, 75, 90 and 100. The primary endpoint is defined as the proportion of participants who achieve PASI75.

To calculate the PASI, the four main body areas are assessed: head (h), trunk (t), upper extremities (u) and lower extremities (l). These correspond to 10, 30, 20 and 40% of the total body area respectively.

The physician quantifies the percentage of the considered body area covered by plaque psoriasis. This percentage of psoriatic involvement is translated into a numerical value "Ax" for each body area: 0 = no involvement, 1 = <10%, 2 = 10 to <30%, 3 = 30 to <50%, 4 = 50 to <70%, 5 = 70 to <90%, and 6 = 90 to 100% involvement. These scores are noted Ah, At, Au, and Al in the formula below.

The signs of severity, erythema (E), induration (I) and desquamation (D) of lesions are assessed using a numeric scale 0-4 where 0 is a complete lack of cutaneous involvement and 4 is the severest possible involvement; scores are made independently for each of the areas, h, t, u and l and represents a composite score for each area. An illustration of judging erythema follows: 0 = no erythema, 1 = slight erythema, 2 = moderate erythema, 3 = striking erythema, and 4 = exceptionally striking erythema.

The PASI score is calculated according to the following formula:

$$\text{PASI} = 0.1(\text{Eh}+\text{Ih}+\text{Dh})\text{Ah} + 0.3(\text{Et}+\text{It}+\text{Dt})\text{At} + 0.2(\text{Eu}+\text{Iu}+\text{Du})\text{Au} + 0.4(\text{El}+\text{Il}+\text{Dl})\text{Al}$$

The PASI score will be set to missing if any severity score or degree of involvement is missing.

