### 8.2.1 Psoriasis area and severity index (PASI)

The PASI is an established measure of clinical efficacy for psoriasis medications (7). The PASI is a tool that provides a numeric scoring for participants' overall psoriasis disease state, ranging from 0 to 72. It is a linear combination of percent of surface area of skin that is affected and the severity of erythema, induration, and desquamation over four body regions.

The endpoints used are based on the percent reduction from baseline, generally summarized as a dichotomous outcome based on achieving over an X% reduction (or PASIX), where X is 50, 75, 90 and 100.

To calculate the PASI, the four main body areas are assessed: head (h), trunk (t), upper extremities (u) and lower extremities (l). These correspond to 10, 30, 20 and 40% of the total body area respectively.

The physician quantifies the percentage of the considered body area covered by plaque psoriasis. This percentage of psoriatic involvement is translated into a numerical value "Ax" for each body area: 0 = no involvement, 1 = <10%, 2 = 10 to <30%, 3 = 30 to <50%, 4 = 50 to <70%, 5 = 70 to <90%, and 6 = 90 to 100% involvement. These scores are noted Ah, At, Au, and Al in the formula below.

The signs of severity, erythema (E), induration (I) and desquamation (D) of lesions are assessed using a numeric scale 0-4 where 0 is a complete lack of cutaneous involvement and 4 is the severest possible involvement; scores are made independently for each of the areas, h, t, u, and l and represents a composite score for each area. An illustration of judging erythema follows: 0 = no erythema, 1 = slight erythema, 2 = moderate erythema, 3 = striking erythema, and 4 = exceptionally striking erythema.

The PASI score is calculated according to the following formula:

$$\text{PASI} = 0.1(E_h + I_h + D_h)A_h + 0.3(E_t + I_t + D_t)A_t + 0.2(E_u + I_u + D_u)A_u + 0.4(E_l + I_l + D_l)A_l$$

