#### 9.2.2.2 *Main analytical approach*

The primary endpoint will be analyzed with the primary estimand defined according to the following attributes:

- Endpoint: Proportion of participants with a 75% or greater PASI score improvement from baseline at Week 12.
- Intervention condition: SAR441566 200 mg BID, 100 mg BID, 200 mg QD, 100 mg QD and 50 mg QD will be compared to placebo.
- Analysis population: NTIP population

- Intercurrent events:
  - The IMP discontinuation: It will be handled with the treatment policy strategy. The primary endpoint will be assessed based on all assessments irrespective of the IMP discontinuation.
  - Starting the selected concomitant medication which could have an impact on the efficacy of IMP: It will be handled with the composite variable strategy. For primary endpoint, participants who receive selected concomitant medications will be considered as non-responders for time points after the medication usage. For other participants, all available data including those collected during the off-treatment period will be used to determine the responder/non-responder status.
- Population-level summary: Difference in the percentage of participants achieving PASI75 response at Week 12 between each active arm and placebo. The Cochran-Mantel-Haenszel test will be used for the primary endpoint analysis. Multiplicity adjustment will be provided (See [Section 9.2.5](#)). Further details will be specified in the SAP.

Missing data will be imputed to non-responders when the response to PASI75 is missing.

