- Population-level summary: Difference in the percentage of participants achieving PASI75 response at Week 12 between each active arm and placebo. The Cochran-Mantel-Haenszel (CMH) test for odds ratio will be used for the primary endpoint analysis, adjusting for baseline disease severity defined by baseline PASI (≤ 20 , >20). The two-sided p-value based on CMH test for odds ratio and 95% confidence intervals (CI) based on Newcombe method (1) for Mantel-Haenszel treatment difference will be presented (SAS code example in [Section 5.4](#)) . Multiplicity adjustment will be provided (See [Section 3.5](#)).
- After applying the rules for the ICEs, the remaining missing data will be handled as follows:
 - Participants will be considered as non-responders.

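### If a severity item is left blank for a clear region, SAP 3.2.1 makes a fully determined PASI missing, and a PASI75 responder is then counted as a non-responder

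*SAP*

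**What the plan says.** SAP 3.2.1 and Protocol 8.2.1 build PASI from four body regions. In each region the sum of the erythema, induration and desquamation scores is multiplied by an area score A and a regional weight. The protocol's formula begins "0.1(E_h + I_h + D_h)A_h + 0.3(E_t + I_t + D_t)A_t". The area score is coded "0 = no involvement, 1 = <10%, 2 = 10 to <30" and so on up to 6. Severity is scored 0 to 4, "where 0 is a complete lack of cutaneous involvement and 4 is the severest possible involvement".

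The missing-item rule in SAP 3.2.1 reads: "The PASI score will be set to missing if any severity score or degree of involvement is missing". It applies to every region alike.

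For missing data that remain after the intercurrent-event rules, SAP 3.2.2 says: "Participants will be considered as non-responders". Protocol 9.2.2.2 agrees: "Missing data will be imputed to non-responders when the response to PASI75 is missing".

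SAP 3.2.3 plans no sensitivity analysis. The single supplementary analysis in SAP 3.2.4 changes how concomitant medication is handled but keeps the same non-responder rule for missing PASI75.

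**The concern.** Severity is multiplied by area, so a region with A = 0 adds nothing whatever its severity scores are. A blank there loses no information about the total, yet the rule discards the total.

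The misclassification runs in one direction. A non-responder whose PASI becomes missing is still a non-responder. A responder whose PASI becomes missing is counted as a failure. Responders are also the participants most likely to have cleared regions by Week 12.

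The planned analyses would not reveal the problem, because the supplementary analysis imputes in the same way. The schedule of activities has one PASI assessment at Week 12 and none at the follow-up visit, so no second planned assessment stands behind it. The same score feeds PASI90, PASI100 and the MCP-Mod analysis. For PASI percent change, SAP 3.3.1.2 would replace the missing value by worst observation carried forward, even when the true value is known and low.

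With 24 participants per arm, single cases are visible in the response rate. Under the step-down order in SAP 3.5, a comparison that fails stops formal testing of those after it.

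**Working it through.** **1. The formula reproduces the stated range.** The SAP says: "The PASI is a tool that provides a numeric scoring for participants' overall psoriasis disease state, ranging from 0 to 72". The maximum severity sum is 3 × 4 = 12, the maximum A is 6, and the weights are 0.1, 0.3, 0.2 and 0.4. The maximum PASI is therefore (0.1 + 0.3 + 0.2 + 0.4) × 12 × 6 = 72, and the minimum is 0.

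**2. A clear region contributes a known zero.** With A = 0, weight × (E + I + D) × 0 = 0 for every severity sum from 0 to 12, in all four regions.

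**3. A constructed participant.**
- Baseline severity sums of 6, 7, 7, 8 (head, trunk, upper, lower) and area scores 2, 3, 3, 4 give 0.1×6×2 + 0.3×7×3 + 0.2×7×3 + 0.4×8×4 = 1.2 + 6.3 + 4.2 + 12.8 = 24.5.
- At Week 12 the head has A = 0 with severity left blank. The other regions each have severity sum 3 and A = 1. PASI = 0 + 0.9 + 0.6 + 1.2 = 2.7, whatever the blanks would have been.
- The reduction is 1 − 2.7/24.5 = 89%, a PASI75 response. The SAP rule gives a missing PASI and so a non-response.
- A participant with A = 0 in all four regions has PASI 0, yet one blank severity item would still make that participant a non-responder.

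**4. Direction.** Let pA and pP be the true response rates on active and placebo, and fA and fP the fractions of responders lost this way. The observed difference is pA(1 − fA) − pP(1 − fP). It is smaller than the true difference whenever pA·fA > pP·fP. With the rates in the SAP 5.5 sample code (0.54 and 0.13), the difference would grow only if fP exceeded 0.54/0.13 = 4.2 times fA. If f is the same in both arms, the difference shrinks by the factor (1 − f).

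**5. Size per case.** One responder is 1/24 = 4.2 percentage points. The counts below are an assumed illustration, tested by an unstratified two-sided Pearson chi-square. The planned test is CMH stratified by baseline PASI, so its p-values would differ somewhat.

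| Active vs placebo | Active responders lost | p |
|---|---|---|
| 11/24 vs 3/24 | 0 | 0.011 |
| 10/24 vs 3/24 | 1 | 0.023 |
| 9/24 vs 3/24 | 2 | 0.0455 |
| 8/24 vs 3/24 | 3 | 0.086 |

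**6. Power over an assumed range of f.** The sample-size rates are redacted, so 13% and 54% are taken from the sample code, with 24 per group, a pooled chi-square test and two-sided 0.05. The documents give no value for f.

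| f | Same f in both arms | Active arm only |
|---|---|---|
| 0 | 87.8% | 87.8% |
| 5% | 84.9% | 83.3% |
| 10% | 81.6% | 78.0% |
| 20% | 74.3% | 65.2% |

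These figures show what a given f would cost. They are not evidence that f is above zero.

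**The case against.** The strongest objection is that the instrument already provides a score for a clear region. Severity runs from 0, that value means no cutaneous involvement, and each area is scored separately. A site that follows the scale enters 0, and the rule then does no harm. The problem needs a data-entry omission, and Protocol 10.1.7 and 10.1.8 provide eCRF completion instructions, quality checking and monitoring for completeness. Inclusion criterion I 02 also obliges sites to produce a PASI at screening and Day 1, when some participants may already have an uninvolved region.

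This stands as a limit on frequency and severity. It does not remove the point, because neither document requires severity to be entered as 0, or filled in automatically, when A = 0.

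A second objection is that complete-item scoring is applied consistently: SAP 3.3.1.1 treats sPGA the same way. But sPGA averages its three items with no area multiplier, so a blank item there leaves the mean unknown. For PASI with A = 0 the total is known.

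A third objection is that any attenuation is conservative for a superiority test. That is broadly right. The exposure is lost power and a flatter dose-response, not a false positive.

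A reader might go further and infer that the rule does bias the primary endpoint against the drug, or that several participants will be lost. The documents do not support either. The eCRF is not among them, and no frequency can be derived.

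**Conclusion.** The point holds in conditional form, at low severity. SAP 3.2.1 discards a score that its own formula determines, and SAP 3.2.2 turns that into a PASI75 non-response. Harm requires that a site leaves severity blank for an A = 0 region, that the blank is not resolved by query, that the participant is a true responder, and that no other complete PASI falls in the Week 12 window (after Day 70).

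The size is 4.2 percentage points per case in an NTIP arm, tending to shrink the difference. The number of cases is unknown and may be zero. It would also be wrong to infer that one or two cases overturn a result: in the example both remain below 0.05, and only the third crosses it. Those counts are assumed.

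**What to change.** Before database lock, replace the missing-item sentence in SAP 3.2.1 with a rule of this kind: a region with area score 0 contributes 0 whether or not its severity items are recorded; PASI is missing only if an area score is missing, or if a severity item is missing in a region with area score above 0. Add that blanks in an A = 0 region are still queried, because they may mean the region was not fully assessed and the 0 was a default.

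The cost is one SAP sentence, one line in the derivation and a data query. The rule imputes no unknown value and leaves the estimand unchanged. If the eCRF already forces or fills in 0, no result changes and the SAP should say so. Adding the rule after unblinding would look data-driven.
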